**LETTER OF AMENDMENT**

DATE: September 09, 2020  
TO: ACTG CTU Principal Investigators, CRS Leaders, and CTU/CRS Coordinators  
FROM: A5380 Protocol Team  
SUBJECT: Letter of Amendment #3 for Protocol A5380

**The following information affects the A5380 study and must be forwarded to each site's institutional review board (IRB)/ethics committee (EC) as soon as possible for their information and review. This Letter of Amendment (LOA) must be approved by the IRB/EC before implementation.**

**The following information may also affect the Sample Informed Consent. The site IRB/EC is responsible for determining the process of informing participants of the contents of this LOA.**

**Upon receiving final IRB/EC and any other applicable regulatory entity approvals for this LOA, sites should implement the LOA immediately. Sites are still required to submit an LOA registration packet to the DAIDS Protocol Registration Office (PRO) at the Regulatory Support Center. Sites will receive a registration notification for the LOA once the DAIDS PRO verifies that all required LOA registration documents have been received and are complete. An LOA registration notification from the DAIDS PRO is not required prior to implementing the LOA. A copy of the LOA registration notification, along with this letter and any IRB/EC correspondence, should be retained in the site's regulatory**

file.

The main reason for this LOA is to provide guidance for the resumption of study visits, in follow-up to the COVID-19-related Clarification Memo #2 (CM #2), dated 04/20/20, as US and non-US sites begin to open to research visits in the presence of the ongoing COVID-19 pandemic. A Study Monitoring Committee (SMC) review occurred on 08/17/20 for the first 10 enrolled participants who were enrolled prior to the temporary closure in March 2020 due to the COVID-19 pandemic. The outcome of the SMC review was that the study may proceed as planned. However, enrollment into the study (i.e., Step 1 entry) will remain paused until approval of this LOA #3, dated 08/26/20.

Follow-up for these 10 enrolled participants remains ongoing with modifications to allow for a mix of virtual and in-person visits. Registration for Step 2 for those already enrolled in Step 1 will resume upon approval of LOA #2, dated 08/14/20.

This LOA is being implemented for the following reasons, per team decision, unless otherwise indicated:

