- The contact information for the Clinical Trials Specialist (CTS) needed to be updated in the roster, and the replacement of one of the statisticians. In response, the following section has been updated: cover page, roster, and study management section.
- Per DAIDS directive, changes made via CM #1, dated 10/15/19, and CM #2 (with additional revisions to reflect the current situation with the COVID-19 pandemic) have been incorporated and remain in bold/strikethrough. In response, the following sections have been updated: 4.1.5, 4.1.7, 4.1.8b, 6.2.3, 6.2.4, 6.3, 6.3.8, 6.3.9, 6.3.10.
- The upper window for Step 2 entry has been extended to 112 days from the confirmation sample. In response, the following sections have been updated: 4.3 (4.3.3, 4.3.5), 6.2.1, and 6.2.4.
- Remote consent for Step 1 and Step 2 is permitted, per local IRB guidance. In response, the following sections have been updated: 6.2.1 and the Sample Informed Consent (SIC).
- The upper window for the Step 1 week 16/SVR12 in-person follow-up visit will remain extended when the study reopens to accrual, per the COVID-19-related CM #2, dated 04/20/20 (extended upper window = +42 days). This visit remains critical for the primary outcome of the study; thus blood sample collection is required within the study window. In response, the following section has been updated: 6.2.3.
- For the Step 1 week 16/SVR12 visit, a virtual visit can be scheduled to conduct all other evaluations with a brief in-person lab visit for blood sample collection. In response, the following sections have been updated: 6.2.3, 6.3.21, and the SIC.
- For the Step 2 SVR12 visit (R+20, R+24, or R+28), the virtual visit should also be paired with a brief in-person lab visit for blood sample collection. In response, the following sections have been updated: 6.2.3, 6.3.21, and the SIC.
- In the event of possible HCV recurrence/virologic failure in Step 1, participants should return to the site within 2 weeks for collection of the HCV recurrence/virologic failure evaluations. All samples should be collected per Table 6.1-1 and stored at the site. In addition, due to COVID-19, for this visit, Liver Function Tests (LFTs), HCV RNA, HCV genotype, and HCV RAS testing, and should be drawn locally for immediate testing. In response, the following sections have been updated: 6.2.4 and the SIC.

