**NOTE: Step 2 entry may be deferred until further notice.**

After the last dose of study drugs, the post-treatment study visits have the following windows:

Step 1 (remote [via telephone] permitted, EXCEPT week 16):

- Study weeks 8 and 12, and 16: -5 days and +21 days
- **Study week 16: -5 days and +42 days**
- Study week 28: -7 days and +28 days

**NOTE: In the midst of the COVID-19 pandemic, for study week 28, all evaluations should be conducted remotely, and the week 28 specimen can be collected at a future date, prior to study closure, up until 36 weeks post treatment completion, as**

~~long as the week 16/SVR12 visit was conducted in person. Participants should only have the week 28 visit in person if the week 16/SVR12 visit and sample were missed.~~

~~If a participant has successfully attended the week 16/SVR12 visit and the blood sample has been collected, then that participant does not need to have an in-person visit at week 28.~~

Step 2 (~~deferred until further notice~~):

- Study week R+20, R+24, or R+28 (12 weeks after re-treatment completion for those not receiving RBV depends on Step 2 treatment duration): -5 days and +28 days
- Study week R+32, R+36, or R+40 completion (for those receiving RBV): -14 days and + 28 days

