**Step 1 (remote, via telephone, EXCEPT week 16):**

- Study weeks 8 and 12, and 16: -5 days and +21 days
- **Study week 16: -14 days and +42 days**
- Study week 28: -7 days and +28 days

**NOTE: In the midst of the COVID-19 pandemic, for study week 28, all evaluations should be conducted remotely, and the week 28 specimen can be collected at a future date, prior to study closure, up until 36 weeks post treatment completion, as long as the week 16/SVR12 visit was conducted in-person. Participants should only have the week 28 visit in person if the week 16/SVR12 visit and sample were missed.**

**If a participant has successfully attended the week 16/SVR12 visit and the blood sample has been collected, then that participant does not need to have an in-person visit at week 28.**

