#### Step 1:

- Study weeks 8, 12, and 16: -5 days and +21 days
- Study week 28: -7 days and +28 days

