## Version History

| Version | Changes Made   | Date Finalized     |
|---------|--|--------------------|
| 1.0     | Original Version per Protocol Version 1.0  | July 11, 2019      |
| 1.1     | Protocol amendment review (V1.0, LOA #1)   | January 2, 2020    |
| 1.2     | Changes due to the study visits affected by COVID-19 outlined in CM #2. Correction of typos. | April 24, 2020     |
| 1.3     | Protocol amendment review (V1.0, LOA #2)   | August 19, 2020    |
| 1.4     | Protocol amendment review (V1.0, LOA #3)   | September 21, 2020 |
| 1.5     | Protocol amendment review (V1.0, LOA #4)   | October 20, 2020   |
|         |  |                    |

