### 1.2 Version History

- Version 1.0 was developed based on Protocol Version 1.0, dated June 07, 2019.
- No changes after review of Protocol Version 1.0, Letter of Amendment #1, dated December 18, 2019.
- Changes due to the study visits affected by COVID-19 outlined in CM #2, dated April 20, 2020. Changes were made in Section 2.5 (HCV interim monitoring), Section 3.1.1 (about primary outcome on SVR12 HCV RNA), Section 3.1.2 (clarification of timeframe) and Section 4.2 first bullet (about HCV RNA data for SVR12 analysis). Typos in 3.1 after asterisk were also corrected. Changes from Version 1.0 are in **bold text**.
- No changes after review of Protocol Version 1.0, Letter of Amendment #2, dated August 14, 2020.
- No changes after review of Protocol Version 1.0, Letter of Amendment #3, dated September 9, 2020.
- No changes after review of Protocol Version 1.0, Letter of Amendment #4, dated October 13, 2020.

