### 3 Outcome Measures

#### 3.1 Primary Outcome Measures

1. [For Primary Objective 1] SVR12 defined as achieving unquantifiable HCV RNA (<LLOQ TD or TND) at the study visit occurring at 12 weeks after treatment discontinuation (week 16). The sample within the visit window for week 12, as defined in Protocol V1.0 Section 6.0, will be used. If a participant does not have any HCV RNA measurements in this time period, then the participant will be considered as SVR12 failure, unless there are preceding and subsequent HCV RNA measurements\* that are both LLOQ (either TD or TND), **or the participants' visit schedule was affected by COVID-19 as outlined in CM #2.**
2. [For Safety in Primary Objective 2] Any reported AE occurring after initiation of study treatment through 4 weeks after the treatment **discontinuation.**
3. [For Tolerability in Primary Objective 2] Tolerability, defined as completion of 4 weeks of treatment without discontinuation due to AEs.

\* The scheduled HCV RNA visits that may be used for the SVR12 determination in case of the missed measurement in the **Week 16** visit window are weeks 8, 12 and 28.

Unscheduled HCV RNA visits may also be used, if applicable. See Section 4.2 below on the analysis approach to SVR12.

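### SAP 3.1 still takes the primary SVR12 window from Protocol V1.0 (-5/+21 days), although LOA #3 set the week 16 window at -5/+42 days for continued accrual

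*SAP*

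**What the plan says.** SAP 3.1 (Primary Outcome Measures, item 1) defines the SVR12 sample: "The sample within the visit window for week 12, as defined in Protocol V1.0 Section 6.0, will be used". Week 12 here must mean 12 weeks after treatment, that is, study week 16, as the footnote to the same section shows. With no sample in the window, the participant is a failure unless the preceding and subsequent results are both unquantifiable, or the COVID-19 clause tied to CM #2 applies. The scheduled visits that may supply those results are weeks 8, 12 and 28; unscheduled samples may also be used. SAP 4.2 adds that the latest preceding and earliest subsequent results are taken. It also gives the conditions of the CM #2 exception: a single post-treatment sample, collected after the window.

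The protocol documents give three windows for the week 16 visit:

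- Protocol V1.0, Section 6.2.3: "Study weeks 8, 12, and 16: -5 days and +21 days".
- CM #2, which limits itself to the 10 participants enrolled by 18 March 2020: "Study week 16: -14 days and +42 days".
- LOA #3, revised Section 6.2.3: "Study week 16: -5 days and +42 days".

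The reasons listed in LOA #3 say: "The upper window for the Step 1 week 16/SVR12 in-person follow-up visit will remain extended when the study reopens to accrual". Its introduction says that "enrollment into the study (i.e., Step 1 entry) will remain paused until approval of this LOA #3", so everyone enrolled later comes under LOA #3. SAP 1.2 records: "No changes after review of Protocol Version 1.0, Letter of Amendment #3, dated September 9, 2020".

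**The concern.** The primary-endpoint rule points to a version of the window that no longer governs most of the trial. With 10 participants enrolled before the pause, at least 34 of the planned 44 (44 - 10) enter under the LOA #3 window. For them a week 16 sample at +22 to +42 days is on schedule under the protocol but outside the window that the SAP names, and the SAP's COVID-19 exceptions do not mention them.

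LOA #3 also makes it possible for such a sample to stand alone. It allows virtual visits at the other follow-up visits and lets research samples wait until the participant returns in person, so HCV RNA at weeks 8 and 12 can be missing. The week 4 result is not on the SAP's list and cannot serve as the preceding value. A later week 28 result does not help either, because a preceding value is still needed.

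In an open-label, single-arm trial with one binomial endpoint, a window left open until results are known would have to be settled by someone who can see which reading helps.

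**Working it through.** **1. The plan's own figures.** The 90% Wilson lower limit is [p + z²/2n - z·√(p(1-p)/n + z²/4n²)] / (1 + z²/n), with z = 1.645.

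- 40/44: p = 0.9091, giving 81.2% (upper limit 95.9%), as in Protocol Table 10.4-2.
- 39/44: p = 0.8864, giving 78.4% (upper limit 94.4%), also as in the table.

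The success rule of 40 or more of 44 is therefore reproduced. Its exact power, P(Bin(44, 0.95) ≥ 40), is 93.3% against the stated 93%.

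**2. The windows in days.** Count from the start of therapy and assume 28 days of treatment, so week 16 is day 112.

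| Source | Window | Study days |
|---|---|---|
| V1.0 | -5/+21 | 107 to 133 |
| LOA #3 | -5/+42 | 107 to 154 |
| CM #2 (first 10 only) | -14/+42 | 98 to 154 |
| Week 28 | -7/+28 | 189 to 224 |

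V1.0 and LOA #3 differ on days 134 to 154. That is (134 - 28)/7 = 15.1 to (154 - 28)/7 = 18.0 weeks after treatment. These days also fall before the week 28 window opens.

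**3. How an unquantifiable sample on days 134 to 154 is scored for a participant enrolled after the pause, with nothing in days 107 to 133.**

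- V1.0 as amended by LOA #3: in window, responder.
- V1.0 literally, where the latest earlier week 8, week 12 or unscheduled result is unquantifiable: the late sample serves as the subsequent result (taken here as an unscheduled sample), so responder.
- V1.0 literally, with no usable earlier post-treatment result: no preceding value and no CM #2 exception, so failure.

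Only the last line differs from the first.

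**4. What one reclassified participant does.** At 44 participants, 40/44 (81.2%) becomes 39/44 (78.4%). At the maximum enrolment of 50, 45/50 (80.8%) becomes 44/50 (78.4%).

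If exactly one true responder among 44 is scored as a failure, the conclusion changes only when exactly 39 of the other 43 respond. The probability is P(Bin(43, p) = 39):

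| True SVR12 | Probability |
|---|---|
| 90% | 20.3% |
| 92% | 19.6% |
| 95% | 10.4% |
| 97% | 3.0% |

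These figures are conditional on one such participant existing. The documents give no rate for that.

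**The case against.** The strongest reply is that V1.0 already means V1.0 as amended. LOA #3 amends Version 1.0 without creating a new version, and the SAP never prints -5/+21. SAP 3.2 and 4.1 cite Protocol Section 6.0 with no version number, so a frozen reading in 3.1 could put two windows on the same sample. On this view, the logged absence of changes after LOA #3 simply means that none were needed. This reading is plausible, and it is why the point is an unresolved rule and not a proven misclassification. But the SAP does not say so. SAP 1.2 identifies Version 1.0 by its June 2019 date, and the version table names the letter when one is meant, as in "Protocol amendment review (V1.0, LOA #3"; that is modest evidence only. The SAP was also edited at this very rule for CM #2, which suggests that schedule changes were thought to need SAP text.

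One might also stretch the CM #2 exception to later participants, since LOA #3 describes its longer window as a continuation of CM #2. CM #2, however, restricts itself to the first 10.

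The case is indeed narrow. After the pause, HCV RNA remains scheduled at weeks 8 and 12, and the restriction to week 16 alone applies only to the first 10. The Analysis Implementation Plan, not available here, may give day limits; the SAP, which defines the outcome, should still agree with it.

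A reader might infer that the first 10 have a matching problem with samples at -14 to -6 days, which CM #2 allowed. The dates do not support this. The last of them entered by 18 March 2020, so day 154 falls on about 19 August 2020, before LOA #3 of 9 September 2020. If the window in force at the visit governs, CM #2 settles those samples. If V1.0 governs, leaving them out is defensible: they lie 10.0 to 11.1 weeks after treatment, and SAP 4.2 accepts only samples taken after the window.

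**Conclusion.** The citation in SAP 3.1 is out of date for participants enrolled after the pause, and the SAP does not settle which window applies to them. The same protocol-compliant, unquantifiable sample is a failure on one reading and a response on the other.

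The conclusion rests on two conditions: V1.0 is read as unamended, and the participant has no usable earlier post-treatment result. The number affected is unknown. A reader might infer that every late sample becomes a failure, or that the planned power is wrong. Neither follows: the bracketing rule recovers most plausible cases, and the 40/44 rule and 93% power stand as stated. The literal reading can only turn responders into failures, so it can lose a true efficacy conclusion but cannot create a false one. The reason to act is that a single participant can decide whether the lower limit clears 80%.

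**What to change.** Before database lock, amend SAP 3.1 so that, for participants enrolled after the pause, the SVR12 sample is the one in the study week 16 (SVR12) window of Protocol Section 6.2.3 as amended by LOA #3, with -5/+42 days written out. Name study week 16 in place of week 12. Leave the first 10 participants to the existing rule and the CM #2 exception in SAP 4.2.

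Do not widen the primary definition to samples at -14 to -6 days. If one of the first 10 has such a sample as the only result, report it in a sensitivity analysis. Check that the Analysis Implementation Plan uses the same days.

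The cost is a wording change and, at most, one sensitivity analysis involving no more than 10 participants; no new data are needed. The downside is that samples up to 18 weeks after treatment count as SVR12, which the amended protocol already allows.

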Participants experiencing documented viral recurrence before or at the week 16 or SVR12 visit will proceed to Step 2 and be classified as either re-infection or suspected relapse, prior to re-treatment. The type of viral recurrence (suspected relapse versus re-infection) will be determined by the A5380 team chair, co-chairs, and virologist ([[contact]](mailto:[contact])) based initially on genotype/subtype information and resistance testing and then reported to the sites by email to inform them of the recommended re-treatment regimen for Step 2. If a re-infection, they will be re-treated with 8 weeks of FDC G/P. If a suspected relapse, they will be re-treated with a treatment regimen of 16 weeks of FDC G/P with or without weight-based RBV, irrespective of genotype. Participants experiencing virologic failure (failure to achieve HCV RNA <LLOQ and confirmed increase in HCV RNA  $>1 \log_{10}$  from nadir) will also proceed to Step 2 and will be re-treated with 16 weeks of FDC G/P with or without weight-based RBV. Participants experiencing post-treatment HCV viremia not otherwise defined as re-infection, suspected relapse or virologic failure will also proceed to Step 2 and will be re-treated with 16 weeks of FDC G/P with or without weight-based RBV. At the discretion of the site PI and upon discussion with the A5380 CMC ([[contact]](mailto:[contact])), participants experiencing suspected relapse, virologic failure, or undefined post-treatment HCV viremia may be re-treated with an alternative, non-study provided regimen. Retreatment options are outlined in the Manual of Procedures (MOPS).

Participants who meet criteria for Step 2, but opt out of therapy will continue study visits on the Step 1 schedule.

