#### Step 2 (8-16-week duration)

Any participant who experiences viral re-infection, suspected relapse, virologic failure, or undefined post-treatment HCV viremia will proceed to Step 2 for re-treatment. Based on both the classification of recurrence and the site PI preference, participants proceeding to Step 2 will be placed on one of the following re-treatment regimens:

Participants with viral re-infection will be re-treated with regimen 2A.

- Regimen 2A:  
Glecaprevir 100 mg/pibrentasvir 40 mg FDC tablet to be taken as 3 tablets orally once daily with food for 8 weeks.

For participants experiencing virologic relapse, virologic failure, or undefined post-treatment HCV viremia (not otherwise defined as re-infection, relapse, or virologic failure), re-treatment options are either regimen 2B or 2C.

- Regimen 2B:  
Glecaprevir 100 mg/pibrentasvir 40 mg FDC tablet to be taken as 3 tablets orally once daily with food, plus RBV 200 mg tablets taken orally twice daily with food. RBV is to be dosed per [Table 5.1.1-1](#) (Weight-based RBV Dose) and [Table 5.1.1-2](#) (Renal Dosing for RBV) with renal dosing superseding weight-based dosing as applicable. Treatment duration is 16 weeks.
- Regimen 2C:  
Glecaprevir 100 mg/pibrentasvir 40 mg FDC tablet to be taken as 3 tablets orally once daily with food for 16 weeks.

The site PI may choose to re-treat these participants with an alternative SOF-based triple DAA regimen in accordance with the local standard of care. The re-treatment regimen choice will be made by the site PI upon discussion with the A5380 CMC. All products for alternative regimens, except for glecaprevir/pibrentasvir, will need to be obtained locally by the site outside of the

study. An example that may use both study product and non-study product is defined in Regimen 2D. Additional possible DAA regimens to be considered for Step 2 can be found in the A5380 MOPS.

- Regimen 2D:  
Glecaprevir/pibrentasvir plus an appropriate third locally-sourced HCV DAA product for a minimum of 12 weeks, administered in accordance with manufacturer's package insert and per site clinician's discretion. The HCV DAA product selected by the site PI must be discussed with A5380 CMC prior to therapy initiation.

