## **2.4 Overview of Sample Size Considerations**

The study is designed to conclude with reasonable evidence that the true SVR12 proportion is greater than 80% in the study population. This will be assessed by examining if a two-sided 90% confidence interval (CI) for the sample proportion is entirely above 80%. This is equivalent to showing that the SVR12 proportion is higher than 80% in a one-sided test with a type I error of 5%. With 44 participants, there is at least 90% power to show that proportion achieving SVR12 is greater than 80% in a one-sided exact binomial test with a targeted significance level of 5%. The true SVR12 proportion is assumed to be 95%, when treated with 4 weeks of the G/P regimen. With a sample size of 44 participants, the Wilson confidence interval for the true SVR12 proportion will be entirely above 80% if 40 or more participants achieve SVR12 out of 44 participants.

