### 4.2 Analysis Approaches

- For the primary analysis:
  - As described in Section 3.1 above on Primary Outcome Measures, if a participant does not have any HCV RNA measurements in the SVR12 visit window, then the participant will be considered SVR12 failure, unless there are preceding and subsequent HCV RNA measurements that are both LLOQ (either TD or TND). The latest available preceding and the earliest available subsequent HCV RNA measurements around the targeted SVR12 visit window will be used. **If the participant's visit schedule was affected by COVID-19 as outlined in CM #2 and (1) only one HCV RNA sample is available after the study treatment, and (2) the sample is collected after the SVR12 visit window, then this result will be used as the primary outcome.**
  - Otherwise, not achieving unquantifiable HCV RNA at the study visit corresponding to the SVR12 evaluation will be considered failure for SVR12 determination in the primary analysis regardless of the reason. As such, early discontinuation of the study prior to the SVR12 visit and reinfection prior to the SVR12 visit will be considered a failure.
  - For the SVR12 analysis, a supplementary analysis will be conducted in the analysis set that excludes (1) participants who discontinued the study for reasons not related to the study treatment, and (2) participants who became re-infected with HCV prior to SVR12 visit. Reasons not related to study treatment may include, but are not limited to: participant moved away, participant cannot get to the clinic, participant cannot be located.
- All available data for the indicated study visits from the participants who initiate the study treatment will be used in the analysis, and the number of participants with available data will be specified for each analysis.
- Confidence intervals around proportions will be provided using the Wilson method for binomial data.

- Subgroup analyses based on the screening HIV infection status will be conducted for the HCV RNA analyses to address Secondary Objective 3.

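### The primary SVR12 rule does not exclude HCV RNA samples taken after further HCV treatment starts, so a rescued Step 1 relapse can, read literally, score as a success

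*SAP*

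**What the plan says.** **Scoring.** SAP 3.1 item 1, which follows Protocol 10.2.1.1, defines SVR12 as unquantifiable HCV RNA at the visit 12 weeks after treatment discontinuation (study week 16). It adds: "The sample within the visit window for week 12, as defined in Protocol V1.0 Section 6.0, will be used". Here week 12 means 12 weeks post-treatment.

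**Missing samples.** Failure by default applies only when there is no HCV RNA result in that period. Exceptions exist for results below LLOQ on both sides of the window and for visits affected by COVID-19. The footnote to SAP 3.1 lists weeks 8, 12 and 28 as scheduled substitutes and adds: "Unscheduled HCV RNA visits may also be used, if applicable".

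**Named failures.** SAP 4.2 counts not being unquantifiable at the SVR12 visit as failure whatever the reason, and continues: "As such, early discontinuation of the study prior to the SVR12 visit and reinfection prior to the SVR12 visit will be considered a failure". It also says that all available data for the indicated visits are used. Relapse, virologic failure, Step 2 entry and non-study HCV therapy are not mentioned. SAP 2.5, by contrast, does count relapse and virologic failure as failures for interim monitoring.

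**Re-treatment.** Protocol 5.1.1 states: "Any participant who experiences viral re-infection, suspected relapse, virologic failure, or undefined post-treatment HCV viremia will proceed to Step 2 for re-treatment". Section 3.0 applies this to recurrence before or at week 16, so re-treatment can begin before the primary endpoint is read. Section 3.0 also provides: "Participants who meet criteria for Step 2, but opt out of therapy will continue study visits on the Step 1 schedule".

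**The concern.** SVR12 is meant to show cure by four weeks of G/P alone. Further HCV treatment that starts before the week 16 sample can make that sample unquantifiable when the four-week course has failed. An endpoint rule for this setting has to say what happens to such a participant, and this one does not. Two routes are open on the wording.

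- **Opt-out.** A participant relapses, declines Step 2, stays on the Step 1 schedule and takes HCV therapy outside the study. The week 16 visit is a genuine scheduled visit, its sample is below LLOQ, and the rule returns success.
- **Step 2 entrant.** A participant enters Step 2 before the window opens. A sample taken on re-treatment then falls inside the window and may be the only one there.

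Either error can only move a participant from failure to success. It also sits oddly beside the other rules. The same person could be a failure for interim monitoring and a success in the primary analysis. Re-infection, which is not a failure of the regimen, is named as a failure, while relapse, which is one, is not.

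**Working it through.** **1. Reproducing the design.** Inputs from Protocol 10.4 and SAP 2.4: n = 44, null value 80%, assumed SVR12 95%, two-sided 90% Wilson interval. The interval "will be entirely above 80% if 40 or more participants achieve SVR12 out of 44 participants".

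The Wilson lower limit is [p + z²/2n − z√(p(1−p)/n + z²/4n²)] / (1 + z²/n), with z = 1.645 and 1 + z²/44 = 1.0615.

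- 39/44: p = 0.8864, centre 0.8640, half-width 0.0796, interval 78.4% to 94.4%. Not met.
- 40/44: p = 0.9091, centre 0.8854, half-width 0.0731, interval 81.2% to 95.9%. Met.

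Both match Protocol Table 10.4-2. The exact power P(X ≥ 40 | 44, p) is 54.7%, 72.6%, 93.3% and 99.0% at p = 90%, 92%, 95% and 97%, against 54%, 72%, 93% and 99% in Table 10.4-1. The exact type I error at 80% is 4.4%.

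**2. Can a sample taken on re-treatment fall in the window?** Days are counted from the start of treatment, with treatment completed on day 28, so week 16 is day 112. R+4 and R+8 are taken at their nominal 28 and 56 days after Step 2 entry (Table 6.1-2).

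| Week 16 window | Days | Entry days with R+4 inside | Entry days with R+8 inside |
|---|---|---|---|
| Protocol V1.0, −5/+21 | 107–133 | 79–105 | 51–77 |
| LOA #3, −5/+42 | 107–154 | 79–126 | 51–98 |

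For entry before day 107, every earlier sample precedes the window, so any sample inside it was taken on re-treatment.

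For entry from day 107, the Step 2 entry sample itself lies in the window. SAP 4.1 uses the result closest to the scheduled week. With entry on day 107 the entry sample is 5 days from day 112 and R+4 (day 135) is 23 days away. With entry on day 126 the distances are 14 and 42 days. The entry sample is therefore the one scored and, if viremic, gives failure correctly. So under LOA #3 too the exposed entries are essentially those before day 107.

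**3. Are such entry days reachable?** HCV RNA is scheduled at week 8 (day 56) and week 12 (day 84). The lag from a first viremic sample to Step 2 entry is an assumption:

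- week 8 detection, 28-day lag: entry day 84, R+4 on day 112, exactly week 16;
- week 8 detection, 14-day lag: entry day 70, R+8 on day 126;
- week 12 detection, 14-day lag: entry day 98, R+4 on day 126.

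All three fall inside even the V1.0 window. The earliest entry days in the table are hard to reach. Entry near day 51 would precede the nominal week 8 visit, and entry also waits for a result (up to two weeks from receipt), a confirmatory sample and, above 1000 IU/mL, genotype and resistance work.

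**4. Effect on the decision.** Let f be the share of true failures scored as success. The documents do not give f, so it is an assumption. At a true SVR12 of 80% the scored success probability is 0.80 + 0.20f, with the 40/44 rule unchanged.

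| f | Scored probability | P(X ≥ 40) |
|---|---|---|
| 0 | 0.80 | 4.4% |
| 5% | 0.81 | 6.1% |
| 10% | 0.82 | 8.3% |
| 20% | 0.84 | 14.6% |

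**The case against.** The best reply is that SVR12 is tied to a visit, not merely to dates. Protocol 8.1.1 separates the Step 1 visits (weeks 8, 12, 16, 28) from the R-numbered Step 2 visits. The SAP footnote lists no R-visit as a scheduled substitute, and re-treatment SVR12 has its own outcome (Protocol 10.2.3.5). Protocol 10.1 says that re-infection before SVR12 is a failure by the definition itself. Re-infected participants also go to Step 2, which suggests that the authors did not expect Step 2 samples to fill the week 16 slot. On this view an early Step 2 entrant simply has no week 16 sample and defaults to failure.

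That is probably the intent for Step 2 entrants, but it is not written down. The default applies only when no HCV RNA was measured in the period, and unscheduled samples are admitted when the scheduled one is missing. The argument does not reach the opt-out participant, who keeps a real week 16 visit.

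The opt-out route can fairly be called uncommon. Alternative regimens are already available within Step 2, and Protocol 6.2.6 envisages that virologic failures who do not enter Step 2 are followed off treatment. That limits the frequency but supplies no scoring rule.

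Two further points stand. Under CM #2 and LOA #3 the first 10 participants were to have Step 1 HCV RNA only at week 16, so earlier detection is unlikely for them. The Analysis Implementation Plan, which is not among the documents, may contain a coding rule. The definition of the primary endpoint nevertheless belongs in the protocol and SAP.

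**Conclusion.** The gap is real and should be fixed; it is a should-fix point. The written rule permits a rescued relapse, virologic failure or undefined viremia to count as SVR12 success. The case is clear for opt-outs treated elsewhere and ambiguous for Step 2 entrants. Re-infection is already covered.

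The number affected cannot be derived from the documents and is probably small: at the planned 95% SVR12 only 44 × 0.05 = 2.2 failures are expected. One participant is nevertheless enough to carry 39/44 across the boundary to 40/44. The rise in false-positive probability to 6.1%, 8.3% or 14.6% rests wholly on the assumed f.

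A reader might infer three stronger things that the documents do not support.

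- **That the plan deliberately credits re-treated participants as cures.** The visit structure and the separate re-treatment outcome point the other way.
- **That the type I error is 10.2%.** That is P(X ≥ 39) at 80%, and it assumes that one failure is rescored in every trial.
- **That Step 2 entry on any of days 51 to 126 is exposed.** From day 107 the entry sample is normally the one scored, and the earliest days are barely reachable.

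**What to change.** Make the same change in Protocol 10.2.1.1 and in SAP 3.1 item 1 and 4.2, so that the two documents do not diverge:

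- A participant who starts any further HCV treatment (Step 2 or non-study) after confirmed recurrence, virologic failure or post-treatment viremia, and before the week 16 sample, is an SVR12 failure.
- Only HCV RNA samples taken before any further HCV treatment may be used for primary SVR12. This includes samples used under the preceding-and-subsequent rule, the unscheduled-sample provision and the COVID-19 exception.

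List these participants in the report with the start date of further therapy.

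The cost is small. Step 2 entry documentation (Protocol 6.3.20) and medication start dates (6.3.7) are already recorded on the eCRF. Sample size and the 40/44 criterion do not change, and the rule keeps its designed 4.4% type I error and 93.3% power at 95%. The one downside is that the SVR12 estimate may become slightly less favourable.
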